Analysis of Data Originally Collected for a Previous Research Study

Behavioral Intervention or Experimentation

Observations

Educational Settings/Assessments/Procedures

Population Based Field Study

Psychophysiological Testing

Deception

Oral History

Interview/Focus Groups

Surveys/Questionnaires/Psychometric Testing

None of the Above

2. * Will any portion of the research be potentially upsetting to the participants:

Yes
 No

3. If Yes, describe the nature of the questions and how you will manage the situation should participants become upset:

Risk of increased distress due to assessment procedures. It is possible that some participants will experience increased intrapersonal or interpersonal psychological distress as a result of participating in assessment or intervention. In the vast majority of cases, we believe that any increased distress experienced will be mild and transitory in nature. If suicidality or large increases in levels of depressive symptoms are detected, the study team will be poised to assess further and make referrals to appropriate community organizations (e.g. Henrico County Community Services Board: [contact]; Chesterfield County Community Services Board: [contact]; Richmond Behavioral Health Authority: [contact]; local emergency departments).

4. Upload ALL instruments/guides that will be used, including scripts/questions to guide interviews, surveys, questionnaires, observational guides, etc.:

ID: MS8_HM20006941

[View: SF - Data Collection Details](#)

Data Collection Details

1. * Select all involved in the study:

Specimen/Biologic Sample Collection

 Protected Health Information (PHI)

 Secondary Data or Specimens Not From a Registry or Repository

 Audio/Video

 Use of Internet for Data Collection

 Registries/Repositories (Includes Accessing, Contributing or Creating)

 None of the Above

2. * Select all identifiers that will be collected as part of this study (including for recruitment, data gathering, data analysis, etc.), even if the data will eventually be anonymized:

Names

 Geographic Locators Below State Level

 Social Security Numbers

 Dates (year alone is not an identifier)

 Ages >89

	Phone Numbers
	
	Facsimile Numbers
	
	E-mail Addresses
	
	Medical Record Numbers
	
	Device Identifiers
	
	Biometric Identifiers
	
	Web URLs
	
	IP Addresses
	
	Account Numbers
	
	Health Plan Numbers
	
	Full Face Photos or Comparable Images
	
	License/Certification Numbers
	
	Vehicle ID Numbers
	
	Other Unique Identifier
	
	No Identifiers
	
	Employee V#
	

3. If "Other Unique Identifier" was selected above, describe the identifiers:

4. * Will participants be able to withdraw their data (paper, electronic, or specimens) from the study if they no longer wish to participate:

Yes
 No

5. If yes above, describe how participants will be able to withdraw their data:

During the informed consent discussion, the study staff will thoroughly discuss the participant's right to drop out of the study at any time, and will provide referrals to any participant upon request. Thus, those who agree to participate will be providing fully informed consent. If a participant chooses to end their involvement with the study, they can contact study staff in any way they choose (written, email, or phone call) and request that their data is withdrawn.

1. * Select all of the types of samples that will be collected as part of this study:

Amniotic Fluid

Blood

Buccal Smears

Saliva

Tissue

Urine

Other

None of the Above

2. If Other, please describe the type of sample being collected:

3. * Describe how the samples will be collected and the collection schedule. For each type of sample, include information about

- The procedures that will be followed to collect the sample
- The role(s) of the individuals who will collect the sample
- The volume/size range of the sample
- The timing and frequency of sample collection

Blood samples will be collected by a trained phlebotomist (PD and/or RA). 8ml blood will be collected by venipuncture in 2 EDTA [purple top] tubes at two points in the study: study visit #1 and study visit #14. The PD and/or RAs will arrange to meet participants to collect the blood in a private, quiet location (most likely research space on the 4th floor of the VCU School of Nursing) and transport samples to the VCU School of Nursing's lab for DNA extraction. Samples will be shipped to HudsonAlpha for DNA methylation assays.

4. * Will Genetic Testing be conducted on any of the samples:

Yes

No

5. * Will any of the samples be used for a pregnancy test:

Yes

No

6. If yes, describe how positive pregnancy results will be communicated to the participant, particularly if minors are involved:

7. * Will any of the samples be used to screen or document alcohol or illicit drug use:

Yes

No

8. * I am aware that I may need to establish a research account with VCUHS Department of Pathology for specimen processing:

Yes

No

ID: MS8_HM20006941

[View: SF - Blood Details](#)

Blood Details

1. * Select all of the methods of sample collection that will be utilized in this study:

Individual Needle Stick(s)

Indwelling Catheter Placed Solely for This Study

Indwelling Catheter Placed for Other Reason(s)

Blood Collected at the Same Time as Non-Research Blood Collection(s)

Unused Blood Originally Drawn for Clinical Purposes

Other

ID: MS8_HM20006941

[View: SF - HIPAA](#)

HIPAA

1. * Describe the protected health information that will be obtained or used in this research:

Participants will self-report past and current medical history, current medications, pregnancy information (gestational age), depressive and other symptoms.

2. * Describe the source(s) of the protected health information:

participant self-report

3. * Explain how the PHI collected or used in this research is the minimum necessary to accomplish this research:

This is the minimum necessary for us to conduct the study and answer our research questions

4. * Select all pathways this research will employ to use or access PHI:

De-Identified Data (none of the 18 identifiers are recorded or associated with the research data)

Limited Data Set

Waiver of Authorization

Partial Waiver of Authorization

Signed Authorization Combined with Consent Form

Signed Authorization as Stand-Alone Form

Partial Waiver of Authorization

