Weekly contact by study staff (phone or email per participants' choice): Study staff will maintain regular contacts in the mode of participants' choice during the 12 weeks of the intervention. This is intended to help with retention as well as monitoring for adverse events. Study staff will collect data about minutes of physical activity during these weekly phone contacts. No survey or other data will be collected during this contacts, unless a participant verbalizes a physical or psychological adverse event.

Study Visit #7 (Intervention Week 6): Participants will be asked to complete questionnaires at the midpoint of the 12-week intervention at home electronically (if they have computer access at home) or in paper/pencil form (for those without sufficient comfort levels or access to a computer~~to~~RA will pick them up at participants~~to~~ next class).

Study Visit #14-- Last visit during pregnancy: Participants will complete another set of questionnaires electronically or in paper/pencil format. A blood sample will also be collected (8 ml blood by venipuncture in 2 EDTA [purple top] tubes).

Study Visit #15-- Postpartum Visit/Interview Session: Each participant will meet with study staff (RA, PD, and/or PI) to complete the questionnaires and participate in a semi-structured interview. Specific questions for this semi-structured interview are found in the Study Interview Guides/Scripts document. This interview will be audiotaped (and later transcribed).

Note: if a participant chooses to withdraw from the study, they will be given the opportunity to give their reasonings for withdrawal in the form of a short interview with research staff.

**** For Addendum Feb 2018: "Long-Term Follow-Up" study visit:** participants who "opted-in" to being contacted for future study will be contacted via email and/or phone about answering survey questions. Participants will give consent via REDCap (or in rare instances, may choose paper & pencil, which will be completed in-person with the research nurse) and will answer survey questions, using the same measures that have been used at previous study visits.

STUDY MEASURES

** SEE TABLE 1. STUDY MEASURES BY TIMEPOINTS

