
Objective Measures: (a) **Epigenetic (DNAm):** Peripheral blood specimens will be collected at baseline (gestation 12-22 weeks) and intervention week 12 (gestation of 24-34 weeks), as summarized in Table 1. The PD and/or RAs will arrange to meet participants to collect the blood and transport samples to the VCU School of Nursing's lab for DNA extraction.

Samples will be shipped to HudsonAlpha for DNA methylation assays. HudsonAlpha will use the following procedures for DNA methylation: genome-wide methylation patterns will be determined using the 450K HumanMethylation Chip (Illumina) according to the vendor's protocol. Briefly, DNA will be extracted from the blood samples using standard techniques (Puregene Isolation Kit; Qiagen). Following bisulfite conversion of the DNA, the methylation patterns of the 485,764 targets (including CpG islands, shores, open sea) interrogated in the 450K array will be determined. To verify the results of the 450K array for targeted regions of interest, single loci methylation-sensitive studies of bisulfite converted DNA will be conducted using standard methods.²⁰⁵ Gene-specific patterns of candidate genes chosen a priori will be closely examined. All samples will be coded prior to deliver to the testing labs. As methylation patterns vary from tissue to tissue, one concern is if the patterns present in white blood cells are reflective of the relevant cumulative epigenetic changes

involved in chronic depressive symptoms. Skepticism regarding the utility of blood for the assessment of conditions having brain/nervous system components has recently been diminished by the observation that comparable DNAm changes induced by environmental/social events occur in multiple tissues.⁷⁵ Based on these findings, Szyf²⁰⁶ noted that the results of recent investigations demonstrate that it is feasible to study behaviorally related DNA methylation signatures in peripheral cells²⁰⁶ (p.334). Given this supporting data, as well as the practical need to collect a minimally invasive specimen for study in this pregnant population, peripheral blood will be used to assess DNAm patterns. (b) Birth weight: At the postpartum visit, mothers will be asked to report the baby²⁰⁶s birth weight.

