above. Findings from this specific aim will provide important preliminary data for future explorations of epigenetic factors involved in treatment response.³⁹

RETENTION AND ADVERSE EVENT MONITORING:

Participants will be contacted weekly by the PD or RA (in the format preferred by participant: phone, text, email) to enhance retention, monitor for any adverse events, and schedule study visits. No data will be collected during these contacts. Participants will be asked if they have any physical or psychological concerns that have arisen and action will be taken if necessary. See protocol for adverse event monitoring in uploaded documents.

5. Upload any supporting tables or documents (e.g. protocol documents, figures/tables, data collection forms, study communications/reminders):

ID: MS8_HM20006941

View: SF - Study Activities

Study Activities

1. * Select which study type best describes the majority of the study. Your response will help determine which IRB panel should review this:

- Bio-Medical
-
- Qualitative - Social/Behavioral/Education (SBE)
-
- Quantitative - SBE
-
- Mixed Method - SBE
-
- Mixed Method - Biomedical
-

2. * This study will involve (check all that apply):

- procedures such as surveys, interviews, field studies, focus groups, educational tests, deception, psycho-physiological testing, any other similar data collection
-
- secondary data analysis: procedures such as analysis of information collected for non-research purposes (includes both retrospective and prospectively collected information), or analysis of data previously collected for a prior research study
- drugs, devices, experimental interventions, biohazards, radiation, other medical or surgical procedures
-

ID: MS8_HM20006941

View: SF - Bio-Med Project Details

Bio-Med Project Details

1. * Select all details that apply:

- Drugs, Biologics, Supplements, and/or Other Compounds
-
- Placebo
-
- Washout Period
-

Device Evaluation

Bio-Hazards, Other Toxins, Recombinant DNA/Gene Transfer

Radiation Exposure and/or Scans involving radiation (PET, MRA)

Stem Cells

Expanded Access - Treatment Use of an Investigational Product

Other Medical or Surgical Procedures

Protected Health Information (PHI)

ID: MS8_HM20006941

View: SF - Social/Behavioral Project Details

Social/Behavioral Project Details

1. * Select all that apply to this study:

Analysis of Information Originally Collected for Non-Research Purposes

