This study will enroll pregnant women who have depression symptoms. Although pregnant women are considered to be a complex or vulnerable population,¹ the National Institutes of Health have stated an objective to encourage research on safe and effective interventions for conditions affecting pregnant women.¹ The self-management intervention is expected to carry less than minimal risk for pregnant participants and no risk to the fetus. No data will be directly collected from the fetus/child; mothers will report the baby's birth weight at the postpartum visit, hence the child is not considered to be a research participant. This study is in compliance with all expectations of research outlined in ²46.46.204 (Additional Protections for Pregnant Women, Human Fetuses and Neonates Involved in Research) of the U.S. Department of Health and Human Services Policy for Protection of Human Research Subjects.²

[name] (PI) has pilot tested the use of a manualized yoga-based PA intervention in a sample of diverse women with moderate-to-severe depressive symptoms; results supported feasibility, acceptability, and short- and long-term

effectiveness.^{18,19,155} We have built upon that study to develop the MOMS intervention by integrating feedback from participants regarding: the length of intervention (we have lengthened the group-based classes from 8 to 12 weeks);¹⁸ and the need for specific knowledge about depressive symptoms and goal-setting to enhance long-term adherence to PA (we have added the nurse-participant partnership and self-guided home PA aspects).¹⁵⁵ We have adapted the group yoga class manual for pregnancy for the MOMS intervention. The PI has recently completed focus groups with pregnant women and new mothers, learning that many women do not receive encouragement from their obstetricians to engage in PA.^{20,137} Moreover, the majority expressed interest in partnering with a healthcare professional to learn about their depressive symptoms and in engaging yoga-based PA as a therapeutic modality for mental and physical well-being.^{20,137} Drs. [name], [name] (Co-I), and [name] (Co-I) have relevant experience with the conduct of randomized controlled trials on health behavior, motivational interviewing, and PA interventions in various populations, including racially and socioeconomically diverse women of child-bearing age, such as those included in this application.¹⁵⁶⁻¹⁵⁹

2. * Select the condition that is applicable to this study [45 CFR 46.204(b)]:

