Individuals who express interest in this study and who meet certain basic inclusion criteria will be scheduled for an in-person meeting with study staff for informed consent and baseline data collection. On the consent form and orally, participants will be given information about: who is sponsoring the study; a description of study procedures; the nature of the assessments; risks and inconveniences; benefits; compensation for study participation; alternative treatment options; confidentiality; the voluntary nature of their participation; and who to contact should they have questions. Consent will be documented through the individual's signature on the consent form. During this discussion, the study staff will also thoroughly discuss the participant's right to drop out of the study at any time, and will provide referrals to any participant upon request. Study staff will also explain that research suggests that participation in a gentle physical activity intervention (e.g., yoga) carries no foreseeable risk to the fetus/neonate. Thus, those who agree to participate will be providing fully informed consent.

8. For children who are pregnant, describe how you will obtain assent from the child and permission from the parent(s) of the pregnant child [45 CFR 46.204(g)]:

n/a

9. * Will inducements, monetary or otherwise, be offered to terminate a pregnancy [45 CFR 46.204(h)]:

Yes
 No

10. * Will individuals engaged in the research have any part in any decisions as to the timing, method, or procedures used to terminate a pregnancy [45 CFR 46.204(i)]:

Yes
 No

11. * Will individuals engaged in the research have any part in determining the viability of a neonate [45 CFR 46.204(j)]:

Yes
 No

ID: MS8_HM20006941

View: SF - VCU Employees

VCU Employees

1. * Describe how the study will minimize the possibility of coercion to participate:

The risk of potential coercion will be minimized by following standard procedures for obtaining informed consent from the participant. The study procedures, risks, benefits, and alternatives will be fully explained to all potential participants. Participants will be aware that they may decline to participate or drop out of the study at any time without any negative repercussions from study staff, health care providers, or affiliated institutions.

ID: MS8_HM20006941

View: SF - Potential Subject Identification and Recruitment

Potential Subject Identification and Recruitment

1. * Choose all recruitment methods that may be used:

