- 8. * Describe criteria for withdrawing an individual participant from the study; such as safety or toxicity concerns, emotional distress, inability to comply with the protocol, etc.:**

We do not anticipate withdrawing a participant from the study, unless she (a) is no longer pregnant due to spontaneous or therapeutic abortion prior to the end of the 12 week intervention period, or (b) she is unable to comply with the protocol and attend a majority of the study sessions, or (c) participant reports any of the following and are advised to cease gentle yoga-based physical activities by their healthcare provider: new vaginal bleeding, new dizziness, new/increased shortness of breath, chest pain, new acute headache, new calf pain/swelling, preterm labor/ delivery (regular, frequent, painful contractions), decreased fetal movement, new fluid leaking from the vagina.

- 9. * Summarize any pre-specified criteria for stopping or changing the study protocol due to safety concerns:**
Participants will be asked to stop engaging in the prenatal yoga classes if they experience any of the symptoms identified by ACOG as reasons to cease physical activity (list in item #8 above). See DSMP.

- 10. Where appropriate, discuss provisions for ensuring necessary medical, professional, or psychological intervention in the event of adverse events to the subjects:**
see data safety monitoring plan

11. * Describe any potential for direct benefits to participants in this study:

We cannot guarantee any direct benefits to participants in the study. The research may yield new knowledge about biobehavioral self-management approaches as adjunctive therapies for perinatal depressive symptoms.

12. * Describe the scientific benefit or importance of the knowledge to be gained:

This study will provide information about the feasibility, acceptability, and preliminary effects of a biobehavioral self-management approach for perinatal depressive symptoms. This line of research will contribute to the body of knowledge about adjunctive therapies for depressive symptoms in pregnancy, a serious problem which contributes to poor maternal-child outcomes. Ultimately, this will contribute to the development and implementation of theoretically driven depression prevention/ resiliency building interventions and measurement of appropriate biobehavioral outcomes to determine the effectiveness of interventions.

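### Birth weight is compared across groups with no gestational age at delivery named, and the displayed text plans no summary of preterm birth or of pregnancy loss after intervention week 12

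*Combined protocol and SAP*

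**What the plan says.** **Contact.** In Research Description, item 4, the paragraph on weekly staff contact places it "during the 12 weeks of the intervention. This is intended to help with retention as well as monitoring for adverse events". On what is recorded, after allowing for minutes of physical activity, it says: "No survey or other data will be collected during this contacts, unless a participant verbalizes a physical or psychological adverse event". The later paragraph on retention and adverse event monitoring describes weekly contact again, with no end date, as being "to enhance retention, monitor for any adverse events, and schedule study visits. No data will be collected during these contacts". It then refers the reader elsewhere: "See protocol for adverse event monitoring in uploaded documents".

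**Birth outcome.** Visit 14 is the last visit in pregnancy. Visit 15, at 6 weeks postpartum, consists of questionnaires and a recorded interview. Under Objective Measures: "At the postpartum visit, mothers will be asked to report the baby", followed by birth weight. The section on pregnant women and fetuses, item 1, agrees: "No data will be directly collected from the fetus/child; mothers will report the baby". No other birth outcome appears in the aims, the measures or the Data Analysis Plan.

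**Use of birth weight.** Specific Aim 2 compares it with archival data, and the Aim 2 analysis correlates it with group. The Comparison Group Data paragraph says that the archival groups are matched on age and race.

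**Events the plan foresees.** Item 8 of the Risks section allows withdrawal of a woman who "is no longer pregnant due to spontaneous or therapeutic abortion prior to the end of the 12 week intervention period". It also allows withdrawal of one whose provider tells her to stop yoga after signs that include preterm labor or delivery and decreased fetal movement. Aim 1 will describe why women leave.

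**The concern.** Birth weight depends on how long the pregnancy lasted and how well the fetus grew. The background section lists growth restriction among the harms of untreated depression, so growth is the part of interest. The comparison group is archival, and nothing in the design balances length of gestation between the groups. Without gestation at delivery, a lower or higher mean birth weight in the intervention group has no clear meaning, and an effect size taken from it for a future trial would carry the same ambiguity.

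The second strand is descriptive safety. The plan itself treats preterm labor and pregnancy loss as things that may happen, yet the analysis plan has no table for them. Women withdrawn for warning signs are among those most likely to have no delivery outcome, because birth weight is asked only at the postpartum visit. The loss criterion in item 8(a) stops at the end of week 12. A woman with a later loss therefore proceeds, as written, to a visit that asks for the baby's birth weight and includes the attachment scale, which postpartum refers to the infant.

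**Working it through.** **1. Reproduce the plan's window.** Objective Measures gives baseline at 12-22 weeks of gestation and week 12 at 24-34 weeks. Check: 12 + 12 = 24 and 22 + 12 = 34. It reproduces.

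**2. Time from week 12 to the preterm limit.** The documents give no limit; 37 weeks is assumed.
- Latest: 37 − 34 = 3 weeks.
- Earliest: 37 − 24 = 13 weeks.

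**3. Time from week 12 to visit 15.** Formula: (gestation at birth − gestation at week 12) + 6. Gestation at birth is an assumption.
- Birth at 40 weeks: (40 − 34) + 6 = 12 to (40 − 24) + 6 = 22 weeks.
- Birth at 37 weeks: 9 to 19 weeks.
- Birth at 41 weeks: 13 to 23 weeks.

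**4. Check against eligibility.** Study Population, item 4, requires only that classes start before 28 weeks. 28 + 12 = 40, so week 12 may fall just short of 40 weeks, outside the 24-34 week window. For such a woman the gap in step 2 vanishes. The gap therefore holds on one passage and not on the other.

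**5. What a birth-weight difference contains.** Write: observed difference = (difference in mean gestation × weight gain per week) + difference due to growth. The plan as displayed measures only the left side. For illustration, assume late gain of 150-250 g per week (not in the documents). A 1-week difference in mean gestation alone gives 150-250 g; half a week gives 75-125 g. Nothing in the documents says that such a difference exists; the point is that it could not be seen.

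**6. What a descriptive summary could show.** With 41 women and assumed preterm rates of 5%, 10% and 15%, the expected counts are 41 × 0.05 = 2.1, 41 × 0.10 = 4.1 and 41 × 0.15 = 6.2. The chance of at least one, 1 − (1 − p)^41, is 88%, 99% and above 99%. Some preterm births are thus likely, and there will probably be something to report.

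**7. Weekly contacts, side by side.** One paragraph records activity minutes, and an adverse event if the woman raises it. The other says that no data are collected. The paragraph on the yoga classes adds that warning signs are assessed at each class and in the weekly calls. These do not agree on what is written down.

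**The case against.** The strongest reply is that the files which would settle the safety strand are not reproduced. The text refers adverse-event detail to an uploaded protocol and to the DSMP, measures to Table 1, and interview questions to the interview guide. All are listed as uploaded. This stands, and it limits what can be claimed. A reader might infer that preterm births and losses will go uncounted; the documents do not support that, only that the displayed text plans no count.

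A reader might also infer that visit 15 asks for birth weight and nothing else. It does not: the questionnaires and open-ended interview could bring out a preterm birth. Nor are losses before the end of week 12 invisible, since they are a withdrawal reason and can appear among the reasons for attrition, though not as a safety outcome.

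Gestation at delivery may be derivable. The HIPAA section lists self-reported gestational age, with no time point, and a visit timed from delivery implies that the date is roughly known. This softens the point, but a variable that might be reconstructed is not one that the analysis plan uses.

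It is also tempting to say that the consent wording must change, because women are told that gentle activity "carries no foreseeable risk to the fetus/neonate". That statement is attributed to research in general and not to this trial's data. The small risk of injury acknowledged elsewhere in the form is not described as fetal. The documents do not show a contradiction here.

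Finally, a pilot of 41 women cannot establish safety. Even 0 events in 41 leaves a one-sided 95% upper bound of 1 − 0.05^(1/41) = 7.0%. At the stated 20-40% attrition, about 33 to 25 women, the bound is 8.7% to 11.3%. This is correct, and the outcomes should be described, not tested.

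**Conclusion.** The point holds in a limited form. As written, the Aim 2 birth-weight comparison cannot tell earlier birth from poorer growth, because gestational age at delivery is not named as a variable for either source and matching covers only age and race. This holds whatever the safety files contain, unless Table 1 adds gestation at delivery and the analysis uses it.

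Separately, no displayed section plans a summary of preterm birth or of loss after week 12, and the only adverse-event contact with a stated duration ends there. On the 24-34 week window that is 3-13 weeks before 37 weeks, and 12-22 weeks before visit 15 for birth at 40 weeks. Both ranges rest on the assumed limits, and neither applies to a woman who starts classes near 28 weeks. This is a cheap improvement to an exploratory comparison and to descriptive reporting; it does not invalidate the feasibility aim.

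**What to change.** - At visit 15, record by maternal report the delivery date, gestational age at delivery, live birth or loss, and adverse events since week 12. Ask the pregnancy outcome first, and skip the birth-weight and infant-attachment items after a loss.
- For withdrawn women, seek the pregnancy outcome through the dropout contact already described under Feasibility and Acceptability Measures.
- In the Data Analysis Plan, report these outcomes descriptively for all enrolled women, and present birth weight together with gestational age at delivery, for the archival groups too if the archive holds it. If it does not, say so and limit the interpretation of the birth-weight comparison.
- Reconcile the 24-34 week window for week 12 with the class-start criterion, and the two paragraphs on what the weekly contacts record.
- If the DSMP, adverse-event protocol, Table 1 or interview guide already collects any of this, cite it in the analysis plan in place of a new item.

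The cost is a few questions at a planned visit, one added question at the dropout contact, and one descriptive table. The limits are recall over roughly 12-22 weeks and a possible lack of delivery gestation in the archive.
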